#### **7.1.3.1.2 Blood Collection for Anti-pembrolizumab Antibodies**

Sample collection, storage and shipment instructions for blood samples will be provided in the Laboratory Manual.

#### **7.1.3.1.3 Laboratory Correlates**

The immunobiologic, neoantigen analyses, advanced studies for minimal residual studies, and flow and ex vivo studies will be performed in collaboration by Drs. [name]'s and [name]'s labs with additional support from [name] lab.

Lab correlates	Assays	Tissue/Body Fluid Tested and Timing of Assay
Immune-antigen repertoire and inhibitory receptor analyses of AML cells and donor T cell exhaustion and functional analyses	Whole exome sequencing of AML at relapse, Flow cytometry, tetramer analyses, cellular killing assays, MHC-peptide binding affinity studies, PCR	PBMC and BM: day 1 (pre-treatment), ±14, 35, 77, ±168, ±252, 365, ±425 , and at relapse/progression
Functional T cell subtypes and cytokine profiles	Flow cytometry: Quantify activated and effector CD4 + and CD8 + cells, NK cells, senescent, exhaustion and regulatory T cells (CD45RA, CD45RO, CD127, CD25, CCR7, CD57, CD28, CD62L, CTLA4, LAG3 and Foxp3)  Cytokine profiling: Intracellular IFN- $\gamma$ (Th1), IL-4 (Th2), IL-17 (Th17), IL-2, and transcription factor profiling with Q-PCR for T-bet, Gata-3, ROR $\gamma$ T, Foxp3	PBMC and BM: day 1 (pre-treatment), ±14, 35, 77, ±168, ±252, 365, ±425 , and at relapse/progression
AML immune peptide repertoire analyses	

• Whole exome sequencing (WES) of relapsed AML blasts

• Characterize neoantigens

• Bioinformatically nominate most immunogenic peptides

• Functionally validate in silico the immunogenic potential of the peptides in the context of the donor MHC

• Functionally validate in vitro the bioinformatically nominated

	
Characterization of T cell exhaustion		

Antigen specific T cell expansion	immunogenic AML peptides by performing MHC-peptide binding affinity assays  PD1, CTLA4, LAG3, TIM3, TIGIT	
Functional Antigen presenting cells  subtypes and cytokine profiles	Tetramer staining for leukemia specific (HLA-A2 + restricted WT1, PRAME, proteinase-3), hematologic cell specific minor antigen specific (HLA-B7 restricted LRH-1), and CMV (pp65).  Quantify CD11c, CD1a, CD14, BDCA3, HLADR, CD40, CD80, CD86 and intracellular IL-1 $\beta$ , TNF $\alpha$ , IL-10, IL-6	
T cell and NK cell cytotoxicity  Plasma cytokines	Intracellular CD107a, granzymeB (flow cytometry), flow cytometric analysis of tumor cell death  TNF $\alpha$ , IL-6, IL-1 $\beta$ , IL-10, Reg3 $\alpha$ , ST-2, TNFR1	PBMC: day 1 (pre-treatment), ~d14 [before 2nd dose of anti-PD-1], 35, 56, 77, $\pm$ 168, $\pm$ 252, $\pm$ 365, $\pm$ 425 and at relapse/progression
Ex-vivo stimulation analyses	Ex-vivo stimulation with specific peptides and DCs with ELISPOT, CFSE and CD107a	PBMC: day 1 (pre-treatment), ~d14 [before 2nd dose of anti-PD-1], 35, 56, 77, $\pm$ 168, $\pm$ 252, $\pm$ 365, $\pm$ 425 and at relapse/progression
AML and MDS post-therapy clonal selection analysis  High-sensitivity response assessment (genomic minimal residual disease detection)	Droplet digital PCR (ddPCR) and single-molecule/real-time (SMRT) sequencing of AML- and MDS-associated mutations in BM, PBMC, and cell-free DNA to: 
 
Define and distinguish responsive and resistant AML clones via longitudinal analysis
 
Assess kinetics and depth of response to therapy at serial timepoints
 
	PBMC and BM: day 1 (pre-treatment), $\pm$ 14, 35, 77, $\pm$ 168, $\pm$ 252, 365, $\pm$ 425 , and at relapse/progression

Sample collection: We will obtain 4 heparinized (green top) and 1 EDTA (purple top) blood samples (or approximately 35 mL total/sample) as well as bone marrow aspirates per schedule shown in the schema above. Buccal swabs will also be collected once prior to initiation of therapy for use as a normal DNA control for each patient. Plasma will be banked and frozen for analysis of anti-PD-1 antibody titers, cytokine analyses, and cell-free DNA as indicated. Leukocytes will be isolated by Ficoll gradient centrifugation and used for phenotypic and functional analyses described below. AML blasts will be analyzed for immune peptide repertoire analyses and as targets for ex vivo studies. For the purposes of this study, day 1 is defined as the first day of pembrolizumab.

**Statistics for correlative studies:** The statistics will be descriptive in nature and hypothesis generating. However the analyses of leukemia from the bone marrow (BM) and both peripheral blood and BM derived

T cells analyses at the time of relapse after allo-HSCT, post treatment with pembrolizumab at 35, 77 and 365 days will nonetheless serve as internal controls for assessing the impact of treatment on relapse, T cell functionality, immune neoantigen repertoire analyses, and depth and kinetics of response. However, the association of the laboratory values and percentage change of each variable and their relation to primary and secondary clinical outcomes will be descriptive and estimated with Cox regression (for response rate and PFS) and competing risks regression (TRM, relapse/progression).

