### 2.2 Trial Diagram

\* standard induction chemotherapy may be administered during induction at investigators discretion if concern for rapid clinical progression of malignancy (see 5.2.1.2).

† Primary study endpoint (s) are ORR (PR+CR) at day 35 and day 77

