#### 3.2.1.1 Exploratory Objectives

- 1) Determine the immunologic correlates of response to checkpoint blockade in patients with hematologic malignancies who have relapsed after allogeneic transplantation via assessment of PD1-PDL1 axis with a well-defined focus on T and NK cell phenotypes, functions and leukemia specific responses.
- 2) Determine the antigenic peptide repertoire of relapsed MDS and AML by whole exome sequencing (WES), bioinformatically nominate the most immunogenic antigens from the WES analyses and then functionally validate the top predicted peptides in silico and in vitro.
- 3) Determine if PD-L1 expression at relapse serves as a biomarker for response to pembrolizumab in hematologic malignancies as has been reported in solid malignancies.
- 4) Identify responsive and resistant malignant clones and assess kinetics and depth of response to treatment with ultrasensitive mutation detection (droplet digital PCR [ddPCR] and single-molecule/real-time sequencing [SMRT])

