#### **Primary objective endpoints:**

Efficacy:

- ORR at days 35 and 77 in subjects receiving pembrolizumab monotherapy
- ORR at day 77 in subjects receiving pembrolizumab  $\pm$  standard induction chemotherapy
- Clinical Benefit Rate (CBR) at days 35 and 77 in subjects receiving pembrolizumab monotherapy

Safety:

- Incidence and severity of GvHD after administration of pembrolizumab
- Grade 3-5 Regimen-related toxicities (RRT) per CTCAE v4
- Incidence of immune mediated toxicities attributable to pembrolizumab

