## **8.0 STATISTICAL ANALYSIS PLAN**

### **8.1 Statistical Analysis Plan Summary**

The statistical plan for this feasibility study of pembrolizumab for relapse after HCT is primarily directed toward the primary objective of safety and feasibility after HCT. The trial will additionally estimate the proportion of patients responding to pembrolizumab monotherapy by overall response rate (ORR). The ORR (CR+PR) will also be estimated at day 35 and 77 for subjects receiving  $\geq$  one dose of single agent pembrolizumab. If progression is noted subjects may receive standard induction chemotherapy. Subjects who are administered standard induction chemotherapy prior to day 77 (for any reason) will be considered non-responders for ORR of pembrolizumab monotherapy. However, we will perform a planned subset analysis to determine the ORR at day 77 for subjects receiving pembrolizumab followed by systemic chemotherapy.

The incidence of grade 3-4 acute GvHD and significant ( $\geq$  grade 3) immune mediated toxicities will be estimated at the conclusion of the treatment period which is 30 days after the last dose of pembrolizumab. Overall survival (OS) and Disease Free Survival (DFS) at 12 months will be calculated by Kaplan Meier methods. The observation period for OS and DFS will begin at the confirmed date of relapse after HCT until death or last scheduled clinical follow up. These observations will assist in determining whether further investigations are warranted after HCT.

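### Cox regression is named for the association of laboratory markers with response rate, but response is a yes/no outcome read at days 35 and 77

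*Combined protocol and SAP*

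**What the plan says.** The paragraph on statistics for correlative studies (Section 7.1.3.1.3) states that "the association of the laboratory values and percentage change of each variable and their relation to primary and secondary clinical outcomes will be descriptive", and then that these associations will be "estimated with Cox regression (for response rate and PFS) and competing risks regression (TRM, relapse/progression"). The samples it has in mind are those at relapse and "post treatment with pembrolizumab at 35, 77 and 365 days". One use of this analysis is the third exploratory objective in Section 3.2.1.1: "Determine if PD-L1 expression at relapse serves as a biomarker for response to pembrolizumab in hematologic malignancies".

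Response itself is set out in several places, always as a proportion at fixed days. The trial diagram notes (Section 2.2) say "Primary study endpoint (s) are ORR (PR+CR) at day 35 and day 77". The primary efficacy endpoints in Section 4.2.2.1 give "ORR at days 35 and 77 in subjects receiving pembrolizumab monotherapy", and Section 8.2.1 repeats this. Section 8.2.2.1 defines CR and PR by blast criteria at a marrow assessment. Section 8.1 adds that subjects who receive induction chemotherapy before day 77 "will be considered non-responders for ORR of pembrolizumab monotherapy". No section defines time to response, a censoring rule for it, or a tie method.

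**The concern.** Cox regression models the hazard of an event over follow-up time. It suits PFS. For a yes/no reading on two planned days there is no event time to model: the date attached to a response is the date of the marrow. A Cox fit would also have to merge the two readings into one time to first response, whereas the plan reports day 35 and day 77 separately. And it would need a follow-up time for subjects started on chemotherapy. Censoring them there would contradict the non-responder rule in Section 8.1.

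What is at stake is how the marker-response results, including PD-L1 at relapse, can be read. As written, the plan does not say what quantity the reported ratio would be, and its default confidence interval would not be that of a comparison of proportions.

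**Working it through.** **No stated figure to reproduce.** The sentence carries no sample size, power or error rate. The check asks what a Cox fit returns when the outcome is binary at a fixed day.

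**Inputs.** From the documents: 20 subjects; response yes/no at day 35 and day 77; windows of ±5 days at day 35 and ±7 days at day 77 in the flow chart (Section 6.0). Assumed, because the documents give no such figures: a marker split 10 high and 10 low, with responder counts *a* (high) and *b* (low) at day 77, and all subjects assigned time 77.

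**Breslow ties, 6/10 versus 2/10.** With one common time, the partial likelihood is θ^6 / (10θ + 10)^8, where θ is the hazard ratio.
- Score equation: 6 = 8 × θ/(θ + 1), so θ/(θ + 1) = 0.75 and θ = 3.0. This equals the risk ratio, 0.6/0.2 = 3.0.
- Information: 8 × 0.75 × 0.25 = 1.5, so SE(log θ) = 1/√1.5 = 0.816. This is √(1/a + 1/b) = √(1/6 + 1/2).
- Correct SE for a log risk ratio: √(1/a − 1/10 + 1/b − 1/10) = √(0.1667 − 0.1 + 0.5 − 0.1) = √0.4667 = 0.683.

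The Cox variance lacks the two −1/10 terms. They belong there because each subject can respond at most once out of a fixed ten.

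**Efron ties, same table.** The score equation is 6 = Σ (j = 0 to 7) of (10 − 6j/8)θ / [(10 − 6j/8)θ + (10 − 2j/8)], solved by θ = 3.84, with SE 0.819. This equals neither the risk ratio (3.0) nor the odds ratio (6 × 8)/(2 × 4) = 6.0.

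**Range over assumed tables** (standard errors on the log scale):

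| Responders, high vs low | Cox, Breslow (SE) | Cox, Efron (SE) | Risk ratio (SE) | Odds ratio (SE) |
|---|---|---|---|---|
| 3/10 vs 1/10 | 3.00 (1.155) | 3.27 (1.155) | 3.00 (1.065) | 3.86 (1.260) |
| 6/10 vs 2/10 | 3.00 (0.816) | 3.84 (0.819) | 3.00 (0.683) | 6.00 (1.021) |
| 8/10 vs 4/10 | 2.00 (0.612) | 2.78 (0.617) | 2.00 (0.418) | 6.00 (1.021) |

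The Breslow SE is too large by 1.155/1.065 = 1.08, 0.816/0.683 = 1.20 and 0.612/0.418 = 1.46 times. The Efron estimate exceeds the risk ratio by 3.27/3.00 = 1.09, 3.84/3.00 = 1.28 and 2.78/2.00 = 1.39 times. Both gaps grow with the response rate.

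**Actual marrow dates.** The windows break some ties, but the resulting order of events reflects when the visit was booked. The fit would then weight responders by appointment day.

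**The case against.** The strongest reply is that Cox regression can be made to work here. With one common time, Breslow ties and a robust variance it returns the risk ratio with a suitable standard error. That is right, so a reader who infers that the PD-L1 objective cannot be answered with the named model goes too far. But the plan states none of those choices.

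A second reply is that the correlative analysis is declared descriptive and hypothesis generating, and that choosing among methods for 20 subjects is partly taste. The low stakes are conceded. A descriptive ratio still needs to be a ratio of something defined.

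A reader might also infer a larger problem: that on-treatment percentage changes are modelled from day 1, so that survivorship biases their association with PFS. The documents do not support that.
- The paragraph gives no time origin and does not say that changes enter as fixed covariates. For OS and DFS the stated origin is different: "The observation period for OS and DFS will begin at the confirmed date of relapse after HCT".
- Nothing says that unsampled subjects count as unchanged. Simulated 20-patient trials with no marker effect do give a median hazard ratio of 0.58 to 0.66 under that coding (assumed one-year event-free rates of 13% to 50%), but the coding is the assumption that produces the result. A fit confined to subjects with a day-77 value who are event-free at day 77 has the same risk sets, and so the same hazard ratio, whether time is counted from day 1 or day 77.
- It is not true that everyone who progresses before day 77 lacks a day-77 value. Sections 5.2 and 5.2.1.2 allow a day-77 assessment after chemotherapy and after progression recorded at day 35.
- Not all markers come from the response marrow. Section 7.1.3.1.3 lists blood assays at about day 14 and day 56.
- PD-L1 at relapse is a pre-treatment marker and needs no landmark.

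**Conclusion.** The model named for response does not match the response endpoint. That follows from the text alone. The numerical size rests on assumed tables with a ten/ten marker split. The model-based standard error is about 8% to 46% too large, and the Efron estimate is 9% to 39% above the risk ratio. The lower end (3/10 versus 1/10) corresponds to 4 responders among 20, so with few responses the practical difference would be small.

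On changes measured during treatment, the plan is silent rather than wrong. A clarification is still worthwhile, because a subject who has already progressed can have a later sample, and a value taken after the event should not predict it.

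This is a minor point. ORR and CBR estimation, the criteria for calling the drug promising (Section 8.2.2) and the toxicity stopping rule (Section 8.2.4) do not use this model.

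**What to change.** In the statistics paragraph of Section 7.1.3.1.3:

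- Replace Cox regression for response rate with exact or Firth logistic regression, one marker at a time, or with Fisher's exact test (categorical markers) and the Wilcoxon rank-sum test (continuous markers). Apply it to response at day 35 and at day 77 separately, keeping the Section 8.1 rule that chemotherapy before day 77 counts as monotherapy non-response.
- Use only markers sampled before the reading: pre-treatment and about day 14 for the day-35 response, with day 35 and day 56 also available for day 77.
- Keep Cox regression for PFS and competing-risks regression for TRM and relapse/progression.
- As a secondary clarification, where on-treatment percentage change is related to PFS, TRM or relapse, either restrict to subjects event-free at the sampling day (a landmark) or enter the marker as a time-dependent covariate. State that pre-treatment markers need neither.

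The cost is one paragraph of text. No new data, visits or samples are needed.

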#### 7.1.4 Other Procedures

##### 7.1.4.1 Withdrawal/Discontinuation

When a subject discontinues/withdraws prior to trial completion, all applicable activities scheduled for the final trial visit should be performed at the time of discontinuation. Any adverse events which are present at the time of discontinuation/withdrawal should be followed in accordance with the safety requirements outlined in Section 7.2 - Assessing and Recording Adverse Events. Visit Requirements

Visit requirements are outlined in Section 6.0 - Trial Flow Chart. Specific procedure-related details are provided above in Section 7.1 - Trial Procedures.

##### 7.1.4.2 Screening

A subject will be considered to be in the "Screening" period from the time he/she signs consent until the date the subject is determined as either "eligible" or "ineligible" (screen failure) by PI or a Co-I. Patients may be consented to this study based on disease eligibility and other criteria at the time of consent, but later removed from the study if the change of disease status makes the subject "ineligible". In the event that this occurs, the subject will be replaced.

##### 7.1.4.3 Treatment Period

**"Treatment Period"** is defined as the first day of pembrolizumab through 30 days after the last dose of pembrolizumab – from 1st to 4th doses (or 17th dose if receiving maintenance). The assessment and reporting period for **adverse events (AE) related to the pembrolizumab** will start from the first pembrolizumab administration until 30 days after the last pembrolizumab administration.

**"Follow-up Period"** is defined as the first day the subject is no longer within the treatment period (e.g. 31 days after last administration of pembrolizumab) until six months after date of initiating study treatment.

##### 7.1.4.4 Post-Treatment Visits

###### 7.1.4.4.1 Safety Follow-Up Visit

The mandatory Safety Follow-Up Visit should be conducted approximately 30 days after the last dose of trial treatment. All AEs that occur prior to the Safety Follow-Up Visit should be recorded. Subjects with an AE of Grade > 1 will be followed until the resolution of the AE to Grade 0-1 or until the beginning of a new anti-neoplastic therapy, whichever occurs first. SAEs that occur within 30 days of the end of treatment or before initiation of a new anti-cancer treatment should also be followed and recorded.

#### **7.1.4.5 Follow-up Visits**

Every effort should be made to collect information regarding disease status until the start of new anti-neoplastic therapy, disease progression, death, end of the study or if the subject begins retreatment with pembrolizumab as detailed in Section 7.1.4.5.1.

Subjects in this trial will not be eligible for retreatment with pembrolizumab beyond the initial study phase.

##### **7.1.4.5.1 Survival Follow-up**

If a subject experiences a treatment related adverse event that necessitates their removal from further study treatment, starts a new anti-cancer therapy (non-protocol defined therapy), does not achieve after induction (phase I), develops progression during maintenance (phase II) or completes planned treatment phase the subject moves from treatment into the survival follow-up phase and will be followed at a minimum of every 8 weeks to assess for survival status until death, withdrawal of consent, or the end of the study (1 year after initiation of pembrolizumab or 90 days after last maintenance dose of pembrolizumab), whichever occurs first (please reference section 5.2.1.2 of this protocol regarding permitted chemotherapies on-protocol). These visits will be coordinated with routine BMT follow-up. If follow-up is not feasible (e.g. patient leaves center) phone contacts will be made every 12 weeks.

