**Secondary objective endpoints:**

- Estimate overall survival (OS) and disease-free survival (DFS) at one year in patients who receive pembrolizumab for relapse after allogeneic HCT.

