Correlative Studies: Blood Collection§, ¶		X	D14 (+5)	D35 (±5)	D56 (±5)		X	D168 (±7) D252 (±7)		X	D425 (±14)†	X
Correlative Studies: Buccal Swabs		X										
Chimerism Analysis (VNTR) (Peripheral Blood)**		X		X			X			X		X

\*Phase II Maintenance treatment: For subjects achieving CR / PR as determined by day 77 response post-induction without significant pembrolizumab related toxicity. Subjects without CR / PR at day 77, relapse / progression after day 77 or clinically significant toxicity during the treatment will be considered off treatment and will be placed into follow-up.

†Follow up: Toxicity assessments will be for 30 days after last dose of pembrolizumab. Longer follow-up for up to 90 days, if applicable, based on continuing SAE / AE that was observed in the treatment period or an events of clinical interest (ECI). Follow up for survival will be up to 90 days after pembrolizumab or D455 (±14) for subjects completing

maintenance and a research blood collection will be obtained. Subjects not initiating or completing maintenance will complete 30 day toxicity assessments and then be followed only for survival (through D365 after initiating pembrolizumab). Subjects in CR/PR not completing maintenance for toxicity may have additional research specimens collected per investigators discretion (see below note). ‡ Relapse denotes collection of unplanned / unscheduled bone marrow aspirate, biopsy and correlative studies at time of clinical suspicion of relapse (if CR) or progression of malignancy at any time during treatment and follow-up periods.

§Bone marrow morphology based on aspirate and/or core biopsy, flow cytometry and  $\pm$  cytogenetics will be performed on day 35 (+5) after dose #2, day 77 ( $\pm$ 7) after dose #4, day 365 ( $\pm$ 14) after completing maintenance. An end of treatment bone marrow may be performed prior to day 365 in subjects in CR/PR who do not complete full maintenance therapy due to toxicity. Subjects removed from further treatment due to documented relapse are not required to undergo further bone marrow studies for research purposes. Cytogenetic analysis may be omitted if there are not pre-treatment cytogenetic anomalies of clinical interest.

||Comprehensive Serum Chemistry Panel should include Magnesium and Phosphorus.

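### Three sections give conflicting ends of follow-up, so it is not settled that every subject is followed to the one-year OS and DFS endpoint

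*Combined protocol and SAP*

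**What the plan says.** The secondary endpoint (Section 4.2.2, secondary objective endpoints) is to "Estimate overall survival (OS) and disease-free survival (DFS) at one year". Section 8.1 gives the method, "Overall survival (OS) and Disease Free Survival (DFS) at 12 months will be calculated by Kaplan Meier methods", and the observation period, which "will begin at the confirmed date of relapse after HCT until death or last scheduled clinical follow up".

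The end of follow-up is set in three places:

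- **Section 7.1.4.5.1** follows subjects who leave treatment until death, withdrawal of consent or the end of the study. A bracket defines the end of the study, and the sentence closes "1 year after initiation of pembrolizumab or 90 days after last maintenance dose of pembrolizumab), whichever occurs first".
- **Section 7.1.4.3** opens the Follow-up Period 31 days after the last dose and runs it "until six months after date of initiating study treatment".
- **Section 6.0, follow-up footnote**: "Subjects not initiating or completing maintenance will complete 30 day toxicity assessments and then be followed only for survival (through D365 after initiating pembrolizumab"). For those who finish maintenance, "Follow up for survival will be up to 90 days after pembrolizumab or D455 (±14) for subjects completing" maintenance.

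Two further sections bear on DFS. Section 5.6 keeps subjects who stop for reasons other than progression in disease-status follow-up until progression, non-study treatment, withdrawal or loss to follow-up. Section 7.1.4.5 asks for every effort to collect disease status. No section says which rule governs.

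**The concern.** A 12-month Kaplan-Meier estimate needs every subject to be observable to 12 months unless something unrelated to prognosis intervenes. Section 7.1.4.3, and Section 7.1.4.5.1 on one reading, stop before that. Section 5.2 ends maintenance early for toxicity or progression, so a cut-off counted from the last dose is tied to prognosis, and censoring at that date could be informative for OS. With 20 subjects, each one carries 1/20 = 5 percentage points of one-year OS.

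DFS has a separate gap. A subject who stops maintenance for toxicity while still in response is followed for survival only under the flow-chart footnote, but for disease status under Sections 5.6 and 7.1.4.5. Whether a later progression in that subject would be captured depends on which section the site follows.

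**Working it through.** **Inputs from the documents.** Dosing every 3 weeks from day 1, with maintenance as doses 5 to 17 from D85 (Section 6.0); the three end rules above; OS and DFS clock from confirmed relapse (Section 8.1). Relapse must be confirmed before entry, so the clock starts before day 1.

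**Calendar check.** Dose k falls on day 1 + 21(k - 1). Dose 5 is 1 + 84 = D85, as the flow chart states. The flow chart's D455 is D365 + 90. Dose 17 is 1 + 336 = D337, so 90 days after the last dose is D427.

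**Section 7.1.4.5.1, earlier-date reading.** Follow-up ends at last dose + 90:

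| Last dose | Day | +90 days | Short of D365 by |
|---|---|---|---|
| 5 | D85 | D175 | 190 |
| 7 | D127 | D217 | 148 |
| 9 | D169 | D259 | 106 |
| 13 | D253 | D343 | 22 |
| 14 | D274 | D364 | 1 |
| 15 | D295 | D385 | not short |

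Doses 5 to 14 therefore fall before D365. The endpoint clock starts at relapse, so if relapse came L days before day 1, 12 months from relapse is about D(365 - L). With L = 14 (assumed) that is D351: a last dose at dose 14 (D364) is covered and one at dose 13 (D343) is not. The exact upper limit depends on L.

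**Section 7.1.4.3.** Six months after day 1 is about D183. If every subject were cut there, no one would be observed to D(365 - L) unless L reached about 365 - 183 = 182 days. For a last dose at dose 8, the Follow-up Period starts at 148 + 31 = D179. For dose 9 it starts at 169 + 31 = D200, after its own end. The definition fails from dose 9 on.

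**Section 6.0.** Follow-up to D365 always covers 12 months from relapse, because relapse precedes day 1.

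**Illustrative size for OS (assumed inputs, not from the documents).** Simulated cohorts of 200,000 used these assumptions:

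- 20%, 30% or 40% enter maintenance, and 50% or 80% of them stop early, with the last dose spread evenly over doses 5 to 14.
- Survival is exponential throughout. The median after an early stop is 60, 120 or 240 days.
- The median without maintenance is 120 days from day 1. For those not stopping early it is 1,000 days from D85.
- Relapse is 14 days before day 1.

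Across the 18 scenarios true 12-month OS ran from 16.7% to 36.8%, and follow-up to D365 reproduced it.

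- *90-day cut-off:* shift of -0.9 to +2.3 points. Highest: 22.6% against 20.3% (40% entering, 80% stopping, median 60 days). Lowest includes 22.8% against 23.7% (20%, 80%, 240 days). The sign turns when early stoppers outlive the other subjects still at risk.
- *Six-month cut-off for off-treatment subjects only, continuing maintenance subjects still followed:* shift of +13.1 to +16.9 points.

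**An extreme case.** Of 20 subjects, 14 die early, three stop at dose 7 and die near D300, and three live past one year. True OS is 3/20 = 15%. With the three stoppers censored at D217, Kaplan-Meier stays at 6/20 = 30%. The 15-point gap arises because every early stopper dies between the cut-off and one year.

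**The case against.** The strongest reply is that the flow chart already settles the matter. Its footnote takes the very subjects at issue to D365, and Section 7.1.4.1 refers to the flow chart for visit requirements. In Section 7.1.4.5.1 the closing phrase can govern the outer list of death, withdrawal and end of study, as the same formula does in Section 5.6. The bracket then gives two dates for two groups: one year for those not completing maintenance, 90 days after the last dose for completers. The earlier-date reading would also end every completer at one year, so the D425 blood sample and follow-up to D455 could never take place. Section 7.1.4.3 sits beside the adverse-event window and is not clearly a survival rule.

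Much of this stands. The two-group reading fits the rest of the protocol better. It does not remove the conflict: Section 7.1.4.5.1 does not limit the 90-day date to completers, the six-month end is in the text without qualification, and nothing gives the footnote precedence. The footnote also leaves the disease-status question open.

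A reader might infer that one-year OS and DFS will be informatively censored and that Kaplan-Meier will overstate both. The documents do not support that. One of the three rules reaches D365. A six-month cut-off for everyone would be administrative, leaving the 12-month estimate unavailable rather than informatively censored. A subject who stops for progression already has the DFS event, so later censoring cannot raise DFS.

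**Conclusion.** The inconsistency is real and should be fixed; bias is conditional on how the text is applied. From the documents alone: the ends of follow-up conflict, the six-month definition is unworkable from dose 9 on, and the earlier-date reading stops at D175 to D364 for a last dose at dose 5 to about dose 14. If that reading were used, censoring could be informative for OS, and for DFS only in subjects who stop without progression. Disease-status follow-up after a toxicity stop is inconsistent under any reading.

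The size and direction of any OS bias rest on assumptions. The scenarios give -0.9 to +2.3 points for the 90-day rule. The larger shift needs the six-month end to be applied to off-treatment subjects only, and 15 points from the 90-day rule is an extreme case. The stakes are moderate: OS and DFS are secondary and descriptive, and neither the criteria for a promising drug (Section 8.2.2) nor the toxicity stopping rule (Section 8.2.4) uses them.

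**What to change.** Reconcile Section 6.0 (follow-up footnote), Section 7.1.4.3 and Section 7.1.4.5.1 to one rule: every treated subject is followed for survival, and for disease status until progression, to at least D365 regardless of treatment status, or to 90 days after the last dose if that is later. In particular:

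- Replace the six-month end in Section 7.1.4.3 with this rule.
- Reword Section 7.1.4.5.1 so that its closing phrase cannot select the earlier of the two dates.
- Amend the footnote so that subjects who stop without progression keep disease-status follow-up, in line with Sections 5.6 and 7.1.4.5.
- Say whether the 90 days run from the last dose (D427 after dose 17) or from D365 (D455).
- State the OS and DFS censoring rules in Section 8.1.

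The cost is wording and a few more status contacts on the existing schedule of every 8 weeks, or 12 weeks by telephone. The largest gap under the 90-day reading is 190 days, and 190/56 is about 3.4, so three or four extra 8-weekly contacts for such a subject.
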